2.3.1. Risk assessment

Potential Risk of Clinical Significance	Summary of Data/Rationale for Risk	Mitigation Strategy
Gepotidacin (GSK2140944)		

Cardiovascular Effects
 
Based on nonclinical data, cardiovascular effects were reversible increases in heart rate and blood pressure (dog and monkey); a reversible 10 to 21 msec (4% to 9%) increase in QTc (monkey); and at the highest dose, a reversible 2 to 3 msec (6% to 8%) increase in QRS (monkey).
 
Based on a thorough QTc clinical study, gepotidacin may cause mild, reversible heart rate effects and QT prolongation.
	
In a thorough QTc study, infusion of gepotidacin at doses of 1000 and 1800 mg over 2 h caused a mild increased heart rate effect of approximately 6 to 10 bpm and QT prolongation measured as $\Delta\Delta QTcF$ of 12 to 22 msec. The QT prolongation evolved during the infusion and was quickly reversed over 2 h after the end of the infusion (see Section 5.2.6 and Section 6 of the IB).
 
In Phase 1 and 2 studies, concentration-dependent QT prolongation has been observed during clinical trials with gepotidacin; however, this increase has not translated into medically significant QTc values or changes from Baseline ($QTcF >500$ msec or change from Baseline >60 msec) or cardiovascular safety concerns.
 
In Phase 1 and 2 studies, gepotidacin did not have a clinically relevant effect on cardiac conduction (PR and QRS intervals).
	
See Section 5.2 for excluded cardiac conditions. Close monitoring of clinical parameters and AEs (Section 1.3) will be conducted, and treatment monitoring and evaluation criteria (Section 7.1.2) will be utilized to mitigate cardiovascular effects.
 
Participants taking medications known to increase QT or potent CYP3A4 inhibitors will be excluded (see Section 6.9.2).
 
See also the Renal and Hepatic sections in this table below.

Potential Risk of Clinical Significance	Summary of Data/Rationale for Risk	Mitigation Strategy

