20. The participant is taking QT-prolonging drugs or drugs known to increase the risk of TdP per the www.crediblemeds.org. “Known Risk of TdP” category at the time of her Baseline Visit, which cannot be safely discontinued from the Baseline Visit (Day 1) through 7 days after the first dose of study intervention; or the participant is taking a strong CYP3A4 inhibitor or a strong P-gp inhibitor.

Cardiac electrocardiogram exclusions

21. The participant has a mean triplicate QTc >450 msec or a mean triplicate QTc >480 msec for participants with bundle-branch block.

Note:

- The QTc is the QT interval corrected for heart rate according to QTcB, QTcF formula, and/or another method. It is either machine read or manually overread.
- The specific formula used to determine eligibility and discontinuation for an individual participant is to be determined prior to initiation of the study. In other words, several different formulas cannot be used to calculate the QTc for an individual participant and then the lowest QTc value used to include or discontinue the participant from the trial.

22. The participant has a documented or recent history of uncorrected hypokalemia within the past 3 months.

Hepatic exclusions

23. The participant has a known ALT value $>2 \times$ ULN.
24. The participant has a known bilirubin value $>1.5 \times$ ULN (isolated bilirubin $>1.5 \times$ ULN is acceptable if bilirubin is fractionated and direct bilirubin $<35\%$).
25. The participant has a current or chronic history of liver disease or known hepatic or biliary abnormalities (with the exception of Gilbert's syndrome or asymptomatic gallstones), including symptomatic viral hepatitis or moderate-to-severe liver insufficiency (Child Pugh class B or C).

Note: Participants with asymptomatic viral hepatitis are eligible for study participation.

Prior antibiotic/antifungal use exclusion

26. The participant has received treatment with other systemic antimicrobials or systemic antifungals within 1 week before study entry.

Concomitant medication use exclusion

27. The participant plans to use any of the prohibited medications or nondrug therapies from the Baseline Visit through 7 days after the first dose of study intervention as detailed in Section 6.9.

Prior/concurrent clinical study experience

28. The participant has been previously enrolled in this study or has previously been treated with gepotidacin.

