6.9.2. Prohibited medications and nondrug therapies

At the time of enrollment and/or during the study from the Baseline Visit through 7 days after the first dose of study intervention, the participant is prohibited from use of the following medications and nondrug therapies:

- An investigational product within 30 days or 5 half-lives, whichever is longer, of the Baseline Visit.
- Treatment with other systemic antimicrobials (e.g., oral ciprofloxacin, amoxicillin/clavulanate, cephalixin, or doxycycline) or systemic antifungals (e.g., oral fluconazole, itraconazole, or terbinafine) within 1 week before study entry. Treatment with systemic fluconazole or other systemic antifungals per local standard of care is only allowed 7 days after the first dose of study intervention.
- Immunosuppressive therapy, including corticosteroid therapy (>40 mg/day prednisolone or equivalent for >1 week, ≥ 20 mg/day prednisolone or equivalent for >2 weeks, or prednisolone or equivalent ≥ 10 mg/day for >6 weeks).
- QT-prolonging drugs or drugs with known TdP risk, per the www.crediblemeds.org “Known Risk of TdP” category, at the time of their Baseline Visit, which cannot be safely discontinued from the Baseline Visit through 7 days after the first dose of study intervention. Details regarding website access and additional guidance are provided in Appendix Section 10.4. Of note, ondansetron is not allowed from the Baseline Visit through 7 days after the first dose of study intervention due to its known TdP risk. Alternative antiemetics that are permitted per investigator discretion are listed in Appendix Section 10.4.

Note: Crediblemeds.org categorizes drugs into 4 categories. The only category for exclusion in this study is the “Known Risk of TdP” category; participants taking drugs that meet criteria of other categories are NOT excluded from participation.

- Strong CYP3A4 inhibitors (a list of strong CYP3A4 inhibitors is provided in Appendix Section 10.4).
- St John's wort or other strong CYP3A4 inducers are not permitted from 14 days before study entry through 7 days after the first dose of study intervention (a list is provided in Appendix Section 10.4).

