- Prescription, nonprescription, or supplements that may impact UTI clinical outcomes including, but not limited to, *Uva ursi*, D-mannose, cranberry tablets, phenazopyridine, NSAIDs including ibuprofen and cyclooxygenase-2 inhibitors, and uricosuric drugs (e.g., probenecid and sulfapyrazone). As described in Appendix Section 10.4, acetylsalicylic acid (doses >100 mg/day) is not permitted.

In addition, antacid preparations containing magnesium trisilicate are prohibited from the start of study intervention at the Baseline Visit throughout the completion of the dosing period (i.e., until all 10 doses of study intervention have been received).

Due to gepotidacin's property of acetylcholinesterase inhibition, the concomitant use of succinylcholine or other nondepolarizing paralytic agents is also prohibited. Caution is to be used in participants who have a condition requiring medication that may exacerbate the inhibition of acetylcholinesterase, or neuromuscular blocking agents.

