Promethazine	Nausea, vomiting
Acetaminophen or paracetamol ^b	Pain, fever
Tramadol ^b	Pain
Hydrocodone ER ^b	Pain, severe
Oxycodone ^b	Pain, severe
Loperamide	Diarrhea
Cetirizine	Antihistamine (H ₁)
Ebastine	Antihistamine (H ₁)
Fexofenadine	Antihistamine (H ₁)

Generic Name ^a	Common Therapeutic Use(s)
Loratadine	Antihistamine (H ₁)
Clindamycin	Antibiotic – topical, nonsystemic only
Neomycin	Antibiotic – topical, nonsystemic only
Polymyxin	Antibiotic – topical, nonsystemic only
Clotrimazole	Antifungal – topical, nonsystemic only
Tolnaftate	Antifungal – topical, nonsystemic only
Ketoconazole	Antifungal – topical, nonsystemic only

a. Check within each local country to assess if other generic names apply.

b. See Section 6.9.1 for details regarding these medications.

Note: See also Section 5.2 for other permitted medications.

List of prohibited concomitant medications:

Generic Name or Category ^a	Common Therapeutic Use(s)
Ondansetron	Nausea, vomiting
Acetylsalicylic acid (doses >100 mg/day)	Pain, other
Celecoxib	Pain
Diclofenac	Pain
Diflunisal	Pain
Etodolac	Pain
Ibuprofen	Pain, fever
Indomethacin	Pain
Ketoprofen	Pain
Ketorolac	Pain
Nabumetone	Pain
Naproxen	Pain
Oxaprozin	Pain
Phenazopyridine	Pain (urinary tract)
Piroxicam	Pain
Rofecoxib	Pain
Salsalate	Pain
Sulindac	Pain
Tolmetin	Pain
Valdecoxib	Pain
Other investigational products	Various
Systemic antibiotics (e.g., ciprofloxacin, amoxicillin/clavulanate, cephalixin, doxycycline)	Antibiotic – all systemic
Systemic antifungals (e.g., itraconazole, fluconazole, terbinafine)	Antifungal – all systemic
Prednisolone or equivalent (refer to Section 6.9.2 for details)	Immunosuppressive therapy
St John's wort	Herbal, various
Uva ursi	Herbal, various
D-mannose	Nutritional supplement, various
Cranberry supplements	Nutritional supplement, various
Probenecid	Uric acid reducer
Sulfinpyrazone	Uric acid reducer
Magnesium trisilicate	Antacid (common ingredient)
Succinylcholine and other nondepolarizing paralytic agents	Muscle relaxation, muscle paralysis

a. Check within each local country to assess if other generic names apply.

Note: See also Section 6.9.2 for other prohibited medications and details for the when these medications are prohibited. All NSAIDs are prohibited; this list may not be an exhaustive list of all NSAIDs available globally.

List of strong CYP3A4 inhibitors:

The list below is not exhaustive and is subject to regular updates as new knowledge emerges and new drugs are approved.

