Strong Inhibitors	
Amprenavir	Ketoconazole
Atazanavir	Nefazodone
Boceprevir	Nelfinavir
Clarithromycin	Ritonavir
Cobicistat	Saquinavir
Conivaptan	Telaprevir
Fosamprenavir	Telithromycin
Grapefruit juice	Troleandomycin
Indinavir	Voriconazole
Itraconazole	

List of strong CYP3A4 inducers:

Rifampin	Ivosidenib
Mitotane	Phenytoin
Avasimibe	Carbamazepine
Rifapentine	Enzalutamide
Apalutamide	St John's wort extract
Lumacaftor	Phenobarbital

List of prohibited antiretroviral medications:

In general, protease inhibitors and non-nucleoside reverse transcriptase inhibitors used for treatment of HIV or hepatitis C are prohibited.

Table of mechanism of antiretroviral-associated drug-drug-interactions:

ARV by drug class	P-glycoprotein	CYP450 inhibition	CYP450 induction	Comments
PK enhancers				
Cobicistat	Inhibitor	3A4 (2D6)		Used as booster
Ritonavir	Inhibitor	3A4 (2D6)		Used as booster
Protease inhibitors				
Atazanavir	Inhibitor/inducer	3A4		
Darunavir	Inducer	3A4		
Fosamprenavir	Inhibitor	3A4		
Indinavir		3A4		
Lopinavir		3A4		
Saquinavir	Inhibitor	3A4		
Tipranavir	Inducer	(2D6)	3A4	
NNRTIs				
Efavirenz		3A4	3A4	
Etravirine			3A4	
Nevirapine			3A4	

Crediblemeds.org instructions

[figure not shown]
Instructions for accessing www.crediblemeds.org and searching for an exclusionary drug due to its “Known Risk of TdP” category are summarized below.

To access www.crediblemeds.org, copy and paste this link into the internet search bar:
<https://www.crediblemeds.org/>

On the main home page, there are 3 search options available. Choose the first option to search for 1 drug at a time. Free registration is required by the website.

Choosing that option brings you to a screen that allows for you to enter a generic or brand drug name and choose Search. If it has a Known Risk of TdP (i.e., is a prohibited exclusionary medication), it will show a red triangle with an exclamation point as shown here:

Search for Drugs that Prolong QT & induce Torsades de Pointes (TdP)

Based on ongoing systematic analysis of all available evidence, CredibleMeds® places drugs into broad categories based on whether each can cause QT prolongation or TdP. These actions are highly dependent on the circumstances of each drug's use AND each patient's clinical characteristics.

Search for Drug of Interest: Zofran Search

Zofran (Ondansetron) - ! Drug has a Known Risk of TdP

[figure not shown]
QT/TdP Risk Categories for Drugs

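### Strong P-gp inhibitors are excluded at entry but missing from the on-study prohibited list, so starting one during dosing breaches no rule unless another provision bars the drug

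*Protocol*

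**What the plan says.** Criterion 20 in Protocol Section 5.2 sits under the Cardiac exclusions and names three drug classes. The first is QT-prolonging or known-torsades-risk drugs that cannot safely be stopped for the first week. The other two are covered by a clause on current use: "the participant is taking a strong CYP3A4 inhibitor or a strong P-gp inhibitor".

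Section 6.9.2 holds the on-study prohibitions. Its window is "At the time of enrollment and/or during the study from the Baseline Visit through 7 days after the first dose of study intervention". The bullet that corresponds to the second part of criterion 20 reads "Strong CYP3A4 inhibitors (a list of strong CYP3A4 inhibitors is provided in Appendix Section 10.4", and P-gp is not mentioned there or in any other bullet.

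Criterion 27 deals with intended use: "The participant plans to use any of the prohibited medications or nondrug therapies from the Baseline Visit through 7 days" after the first dose. It defines the prohibited drugs by reference to Section 6.9.

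The prohibited list in Appendix 10.4 does not name the P-gp class. P-glycoprotein appears in that appendix only as a mechanism column in the table titled "Table of mechanism of antiretroviral-associated drug-drug-interactions".

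**The concern.** An interaction that justifies exclusion at entry would ordinarily matter at least as much while the drug is being taken. Here the protocol restricts the class at the moment of enrollment and then says nothing about it for the dosing period. A patient taking a strong P-gp inhibitor at Baseline is ineligible. A patient who starts the same drug the next day breaks no rule, provided no other provision covers it.

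Three features of the study make a written rule useful:

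- Nine of the ten doses are self-administered at home (Section 1.3).
- The only ECG the protocol requires is at Baseline (Sections 7.1.2 and 8.3.3), so none is scheduled after a mid-course start.
- SAP Section 6.1.4 summarises prohibited non-antibiotic medications separately, and a class absent from the prohibited list would not naturally be counted there.

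What is at stake is a small point of participant safety and of consistent deviation reporting. The efficacy estimates are not involved.

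**Working it through.** No figure in the plan needs reproducing. The check sets the rules side by side.

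| Provision | What it governs | QT / known torsades risk | Strong CYP3A4 inhibitors | Strong P-gp inhibitors |
|---|---|---|---|---|
| Criterion 20 (5.2) | Use at entry | Named | Named | Named |
| Section 6.9.2 | Use at enrollment and from Baseline through 7 days after first dose | Named | Named | Not named |
| Criterion 27 (5.2) | Planned use in the same period | Through 6.9 | Through 6.9 | Not reached |
| Section 2.3.1, cardiovascular mitigation | Summary of exclusions, citing 6.9.2 | Named | Named (as potent) | Not named |

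**Step 1, classes.** Criterion 20 names 3 classes and Section 6.9.2 carries 2 of them, so 3 − 2 = 1 is omitted. There is no blacked-out text in either criterion or in Section 6.9.2, so redaction does not explain the omission.

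**Step 2, drugs the documents themselves mark as P-gp inhibitors.** The antiretroviral table in Appendix 10.4 marks five: cobicistat, ritonavir, atazanavir (inhibitor/inducer), fosamprenavir and saquinavir. All five are on the strong CYP3A4 inhibitor list in the same appendix. The number marked there that escape is therefore 5 − 5 = 0.

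**Step 3, other rules that may catch a P-gp inhibitor.**

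- The strong CYP3A4 inhibitor list is open: "The list below is not exhaustive and is subject to regular updates as new knowledge emerges and new drugs are approved".
- Appendix 10.4 bars, in general, the protease inhibitors and non-nucleoside reverse transcriptase inhibitors used for HIV or hepatitis C.
- Section 6.9.2 bars known-torsades-risk drugs, systemic antimicrobials and antifungals, and immunosuppressive therapy.
- One further bullet is open-ended, "Prescription, nonprescription, or supplements that may impact UTI clinical outcomes including, but not limited to" the products it lists, but it is tied to urinary outcomes and not to drug interaction.

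None of these is a rule about P-gp inhibition. What remains is any strong P-gp inhibitor that falls under none of them. The antiretroviral table is not a general list of P-gp inhibitors and the protocol supplies no such list, so the size of the remainder cannot be derived from the documents.

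**Step 4, clinical weight.** Section 2.3.1 says that in Phase 1 and 2 "concentration-dependent QT prolongation has been observed during clinical trials with gepotidacin; however, this increase has not translated into medically significant QTc values". No passage reports what P-gp inhibition does to gepotidacin concentration.

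**The case against.** The strongest reply is that no drug has been shown to fall in the gap. The five that the protocol marks are all barred already, several other rules overlap, and naming a drug that escapes would need pharmacology from outside the documents. That is correct, and it limits how much weight the point can bear.

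The second reply concerns intent. The mitigation text in Section 2.3.1 agrees with Section 6.9.2 in naming only QT drugs and potent CYP3A4 inhibitors, so the P-gp phrase in criterion 20 could be the stray one, and deleting it would also reconcile the text. The documents do not settle this. However, a risk summary does not override a binding exclusion criterion. Criterion 20 names P-gp inhibitors separately, and nothing explains why the class should be barred at entry and allowed during dosing.

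The reading of P-gp inhibition as a cardiac concern is also an inference from the heading over criterion 20. That stands as a limit on the argument.

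There are backstops too. Concomitant medication is reviewed throughout (Section 1.3, footnote t), questions go to the medical monitor (Section 6.9), and the investigator may stop study drug at any time (Section 7.1). Treatment lasts only 5 days. These reduce the risk, but each depends on someone noticing a problem that Section 6.9.2 does not flag, and none makes the start a prohibited use.

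**Conclusion.** The mismatch is real and the concern holds. One of the three drug classes in criterion 20 is not carried into the on-study prohibition, and criterion 27 does not repair this. The practical reach is small: none of the 5 P-gp inhibitors marked in Appendix 10.4 escapes, and the qualifier that another rule may bar a given drug is needed.

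No change in risk can be calculated, because the documents give neither the exposure effect nor the frequency of such starts. The primary analysis, the secondary analyses and the sample size are untouched. This is a desirable tidy-up and not a defect that threatens the trial.

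The conclusion assumes that the Appendix 10.4 lists available are complete. A few pages near the end of that appendix, among the CredibleMeds and protocol-inquiry instructions, were not available. The omission from Section 6.9.2 does not depend on them.

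**What to change.** Extend the CYP3A4 inhibitor bullet in Section 6.9.2 to cover strong CYP3A4 inhibitors and strong P-gp inhibitors, under the existing window of Baseline through 7 days after the first dose. Criterion 27 then covers planned use without any edit, because it points to Section 6.9. A short reference list of strong P-gp inhibitors in Appendix 10.4 would help sites but is optional.

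If the sponsor holds interaction data showing that the class does not matter during dosing, the protocol should say so and criterion 20 should be reconsidered to match.

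The cost is a few words in one bullet, and one more class of concomitant drug withheld for about a week. Visits, sample size and analysis do not change.

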5.3. Lifestyle considerations

- Participants will be requested to abstain from sexual activity from the Baseline Visit through 7 days after the first dose of study intervention to prevent possible re-infection.

5.3.1. Meals and dietary restrictions

Study intervention is to be taken after food consumption (a meal or a snack) and with water (see Section 6.1).

5.4. Screen failures

Screen failures are defined as participants who consent to participate in the clinical study but are not subsequently enrolled. A minimal set of screen failure information is required to ensure transparent reporting of screen failure participants to meet the Consolidated Standards of Reporting Trials publishing requirements and to respond to queries from regulatory authorities. Minimal information includes demography, screen failure details, eligibility criteria, any protocol deviations, and any SAEs.

Participants who are screen failures are allowed to be rescreened once for the same infection episode or a subsequent infection episode and participate in the study if they meet all of the inclusion and exclusion criteria.

5.5. Criteria for temporarily delaying enrollment/randomization/administration of study intervention

Not Applicable.

6. STUDY INTERVENTION AND CONCOMITANT THERAPY

Study intervention (used interchangeably with study treatment) is defined as an investigational product intended to be administered to a participant.

6.1. Study intervention administered

All doses of study intervention are to be taken after food consumption and with water. Participants will receive oral study intervention (gepotidacin [2 × 750 mg tablets]) BID (approximately every 12 hours) for 5 days. Doses are to be taken approximately 12 hours apart, but the allowable window is 6 to 14 hours. There must be at least a 6-hour minimum window between doses. The first oral dose will be administered at the study site at Baseline; participants will self-administer subsequent doses as outpatients thereafter.

Each treatment day will be assessed over a 24-hour period, starting with the first dose of study intervention received for an individual participant. For example, participants who only receive 1 dose of study intervention on their first calendar day in the study due to a late afternoon/evening Visit 1 will take the second dose on the following calendar day, which will complete Day 1. This pattern will continue until all 10 doses are received; thus, the tenth/last dose will be taken prior to Visit 5 (may be 5 or 6 calendar days, depending on when the first dose is taken).

Gepotidacin tablets (750 mg) are not to be broken and must be swallowed whole. The dosage schedule must always encourage study intervention to be taken as close to 12 hours apart as possible.

Table 3 Study intervention administered

Intervention Name	Gepotidacin
Intervention Description	Administer BID (every 12 hours) for 5 days: 1500 mg as 2 × 750 mg tablets for a 3000 mg total daily dose Each dose is to be taken after food consumption and with water
Type	Drug
Dose Formulation	Tablets containing gepotidacin and inactive formulation excipients
Unit Dose Strength	750 mg tablets
Dosage Level	1500 mg BID
Route of Administration	Oral
Use	Investigational
Sourcing	Provided centrally by GSK ^{CCI}
Packaging and Labeling	Gepotidacin tablets will be provided in bottles with required labeling
Manufacturer	^{CCI} [REDACTED]

The supply and shipping of the study intervention will be supported by Xpress.

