- q. The first dose of study intervention will be administered at the study site during Visit 1; the remaining 9 doses over the 5-day treatment course will be self-administered as outpatients. Each dose is to be taken after food consumption and with water to assist with tolerability. The third dose of study intervention cannot be taken until the Visit 2 assessments have been completed.
- r. Record SAEs from the start of study intervention. However, SAEs assessed as related to study participation or related to GSK product (non-IMP) will be recorded from the time of consent/assent. See Section 8.4.1 for details. During any postbaseline visit, if a participant reports an SAE, VRCC will refer the participant to the study site to record the SAE.
- s. Record AEs from the time of the first dose of study intervention. During any postbaseline VRCC telephone calls, if a participant reports an AE, VRCC will refer the participant to the study site to record the AE.
- t. Prior and concomitant medications will be collected and reviewed throughout the study. During any postbaseline visits if a participant reports concomitant medication use, VRCC will refer the participant to the study site to record the concomitant medication.
- u. Study intervention compliance will be determined via telephone on a daily basis. VRCC will ask the participant how many tablets have been taken and/or are remaining. Participants will return study intervention to the study site by Visit 7 using a prepaid envelope provided by the study site.
- v. Schedule the date and time of the next telephone visit.

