4.4. End-of-study definition

A participant is considered to have completed study intervention if the participant has taken all doses of the study intervention (1500 mg BID taken as 2 × 750 mg tablets for a total of 10 doses). A participant is considered to have completed the study if the participant has completed all study visits including Visit 7 (Follow-up/Day 28).

The end of the study is defined as the date of the last visit of the last participant in the study.

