6.5. Study intervention compliance

- When participants are dosed at the study site during the Baseline Visit, they will take their study intervention when directed by the investigator or designee, under medical supervision. The date and time of any dose administered at the study site will be recorded in the source documents. The dose of study intervention and study participant identification will be confirmed at the time of dosing by a member of the study site staff other than the person administering the study administration.
- When participants self-administer study intervention as outpatients, compliance with gepotidacin will be assessed through querying the participant during the telephone On-treatment Visits (Visit 2 [24 hours \pm 4 hours], Visit 3 [48 hours \pm 4 hours], Visit 4 [72 hours \pm 4 hours], and Visit 5 [96 hours \pm 4 hours]) and documented in the source documents and eCRF. In addition, a record of the number of gepotidacin tablets dispensed to and returned by each participant must be maintained and reconciled with study intervention and compliance records. Study intervention start and stop dates, including dates for intervention delays, will also be recorded in the eCRF.

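### Four sections place the tenth dose before Visit 5 (96 ± 4 h), but dosing as near 12-hourly as possible puts it at about 108 h, after that window has closed

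*Protocol*

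**What the plan says.** Protocol 6.1 prescribes a dose about every 12 hours for 5 days, allows gaps of 6 to 14 hours, and adds: "The dosage schedule must always encourage study intervention to be taken as close to 12 hours apart as possible". Protocol 4.4 counts a complete course as two tablets twice daily "for a total of 10 doses".

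The sentence at issue in 6.1 reads "thus, the tenth/last dose will be taken prior to Visit 5", with the bracket "may be 5 or 6 calendar days, depending on when the first dose is taken". It also stands in Protocol 1.3 (footnote d), Protocol 4.1 and SAP 1.2; Protocol 4.1 writes the 96 ± 4 h window into it. The example that leads up to it in 6.1 is a participant with a late first visit, who "will take the second dose on the following calendar day, which will complete Day 1".

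Visit windows run from the first dose (Protocol 1.3). Footnote q adds: "The third dose of study intervention cannot be taken until the Visit 2 assessments have been completed".

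On compliance, Protocol 6.5 says "compliance with gepotidacin will be assessed through querying the participant during the telephone On-treatment Visits", meaning Visits 2 to 5. Footnote u specifies: "VRCC will ask the participant how many tablets have been taken and/or are remaining". The Visit 5 text in Protocol 8 still has participants dosing 12-hourly. It then has them pack their bottles after the call and send them to the site before Visit 7.

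**The concern.** The sentence about the tenth dose is an operative statement in the schedule of activities, the design section, the dosing section and the SAP. It does not fit the dosing interval set in the same section.

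Staff who take it literally can go wrong in two ways. They may encourage gaps shorter than the 12 h target so that the course ends before the call. Or they may treat a fully adherent participant who still holds tablets at Visit 5 as non-compliant, or as finished, just before she packs her bottles. At stake are the last one or two doses of a ten-dose course, and how cleanly they are recorded.

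**Working it through.** **Inputs**
- Ten doses, hence nine gaps (Protocol 4.4).
- Target gap 12 h, allowed gap 6 to 14 h (Protocol 6.1).
- Time zero is the first dose; Visit 5 is at 96 ± 4 h, that is 92 to 100 h (Protocol 1.3).
- Dose 3 follows Visit 2, which is at 24 ± 4 h (Protocol 1.3).

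**1. Time of each dose.** Dose k falls at (k − 1) × 12 h.
- Dose 8: 84 h. Dose 9: 96 h. Dose 10: 108 h.
- Doses taken before 92 h: 8. Before 96 h: 8. Before 100 h: 9.
- Dose 10 comes 108 − 96 = 12 h after the target time of Visit 5 and 108 − 100 = 8 h after the window closes.

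The plan's statement is therefore not reproduced. Holding dose 3 does not rescue it. If dose 3 were taken the moment Visit 2 ended, at 20 or 28 h, then 7 × 12 = 84 h more puts dose 10 at 104 or 112 h, still after 100 h. Footnote q sets only an earliest time for dose 3, so 24 h is the natural reference.

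**2. Gaps needed to finish before Visit 5.**
- Mean over all nine gaps: 92/9 = 10.2 h, 96/9 = 10.7 h, 100/9 = 11.1 h.
- With dose 3 at 24 h and a call at 96 h, mean over the last seven gaps: (96 − 24)/7 = 10.3 h.

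These lie inside the 6 to 14 h tolerance but are persistently shorter than the target.

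**3. Calendar days.** Let the first dose be at clock hour t on day 1, with t below 24. Calendar day 6 begins 120 − t hours later.
- A day-6 dose before 96 h needs 120 − t < 96, so t > 24: impossible.
- A day-6 dose before 100 h needs t > 20: a first dose after 20:00 and a call at the very end of the window.
- A dose at 108 h is on day 5 if t < 12 and on day 6 if t ≥ 12.

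The bracket about five or six days thus fits 108 h exactly, and its six-day case contradicts the statement it is attached to. The late-start example agrees: one dose on day 1 and two a day after that give 1 + 2 + 2 + 2 + 2 = 9 doses by the end of day 5, and the tenth on day 6.

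**4. Other text pointing the same way.** Treatment days in 6.1 are 24-hour periods from the first dose, and the second dose completes Day 1. Doses 9 and 10 then belong to Day 5, which runs from 96 to 120 h. The schedule of activities marks dosing in the 96 h column, and the Visit 5 text keeps participants on 12-hourly dosing. None of this fits a course already finished.

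**5. What is outstanding at Visit 5.** On schedule, 10 − 8 = 2 doses (4 tablets of the 10 × 2 = 20 in the regimen), or 10 − 9 = 1 dose (2 tablets) once dose 9 has been taken. The number of tablets dispensed is not stated, so the count left in the bottle could be higher.

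**The case against.** The strongest reply is that this is a wording slip with safeguards around it. Much of that stands.
- The 6 to 14 h tolerance makes a finish before Visit 5 permissible, and only the six-day case of the bracket conflicts outright. But the sentence states what will happen, not what may, and the same section steers dosing toward 12 h.
- Protocol 6.5 requires dispensed and returned tablets to be counted and reconciled with the compliance records, and stop dates to be entered in the eCRF. A reader might infer that the tenth dose goes untracked; the documents do not support that. Only the visible telephone query misses it, and since the Visit 6 text is redacted, a query there cannot be ruled out.
- The Visit 5 list tells participants to keep dosing before it reaches the packing step, and the return deadline is Visit 7. There is time to finish. What is missing from the visible text is an explicit instruction to do so before packing.

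Two further inferences are tempting and should not be drawn.
- **Adverse events related to acetylcholinesterase inhibition.** SAP 4.5.2.1.3 times their window from the last dose, so one might claim that hours of it are lost. The eCRF dose-time fields are not visible, and that SAP section refers to an end date and time of treatment, so no loss can be shown or sized.
- **The evaluable set at 96 h.** With 10 planned doses, a participant who missed one would have 7/10 = 70% and fall below the 80% threshold; with 8 planned doses she would have 7/8 = 87.5% and qualify. But the formula for compliance up to each timepoint is redacted in SAP 6.1.6, so which denominator applies is unknown. A participant with no missed dose reaches at least 8/10 = 80% either way.

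**Conclusion.** Wrong as written; minor. On the prescribed schedule the tenth dose falls at about 108 h, some 8 h after Visit 5 closes, and a fully adherent participant has one or two doses left at the last visible telephone compliance query. This rests on gaps held close to 12 h and dose 3 at about 24 h.

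The primary endpoint, assessed at 24 h, is unaffected, and no effect on any other analysis is demonstrated. The practical risk is confined to shortened dosing intervals, misread adherence at Visit 5, and bottles packed before the course is complete.

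**What to change.** - In Protocol 1.3 (footnote d), 4.1 and 6.1 and SAP 1.2, state that 8 doses (at most 9) are due before Visit 5 and that the last is due at about 108 h, on calendar day 5 or 6.
- In the Visit 5 text of Protocol 8, instruct participants to finish the remaining doses before packing the bottles.
- If neither the redacted Visit 6 text nor the eCRF already provides for it, record at the Visit 6 call the date and time of doses taken after Visit 5.

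The cost is one corrected sentence in four places, one added instruction, and at most one question on a call that is already scheduled. No visit, procedure or analysis changes.
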